- Treatment of interest: the randomized treatment (secukinumab or placebo)

The intercurrent events will be handled as follows:

- 1. Discontinuation of study treatment due to any reason (including AE and lack of efficacy): if participants discontinue study treatment due to any reason (including AE and lack of efficacy), the event will be ignored (treatment policy)
- 2. Prohibited medication: if participants receive prohibited medication without study treatment discontinuation, the event will be ignored (treatment policy)
- 3. Rescue medication: if participants take rescue medication without study treatment discontinuation, the event will be ignored (treatment policy)

Summary measure: difference in proportions between treatments

4 Study design

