## 2.6.2 Statistical hypothesis, model, and method of analysis

The secondary objectives will be analyzed in a purely descriptive manner. Categorical variables will be presented in frequency tables. PROMIS change from baseline over time will be presented by treatment group using a summary table. No testing strategy will be applied.

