## 3.2 Secondary endpoint(s)

The estimated power with the chosen sample size based on data from the POC study are summarized in Table 3-1 and Table 3-2.

Table 3-1 Summary of power for continuous secondary endpoints

Endpoint	Mean difference	SD	Power
PROMIS SF UE  at Week 16	1.2	3	84%
WORC PSD at Week 24	14	30	95%

 $^{1}$  Considering the missing data due to potential PROMIS SF UE translation issues in China , N = 110 per treatment group was used for the power calculation.

Table 3-2 Summary of power for binary secondary endpoints

Endpoint	Response Rate		Power
	Secukinumab (N=117)	Placebo (N=117)	
WORC-PSD40  at Week 16	60%	35%	97%
WORC-TOT50  at Week 16	50%	25%	97%
WORC-PSD40  at Week 24	60%	35%	97%

<sup>1 WORC-PSD40: Proportion of participants achieving an increase of at least 40 points from BSL in WORC PSD score

<sup>2 WORC-TOT50: Proportion of participants achieving an increase of at least 50 points from BSL in WORC total score

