#### 5.4 Statistical models

#### 5.4.1 Summary statistics for binary and categorical data

Summary statistics for discrete variables will be presented in contingency tables and will include count and frequency in each category. If applicable, confidence intervals will be derived as well based on the score method including continuity correction (Newcombe 1998):

With z as  $(1-\alpha/2)$ -quantile of the standard normal distribution (SAS:  $z = probit(1-\alpha/2)$ , n as total number of participants (i.e., number of participants in the denominator), p as estimated crude incidence (number of participants with event / n) and q = 1-p

Then the lower limit is

$$L = 100 \times \max \left(0, \frac{2np + z^2 - 1 - z\sqrt{z^2 - 2 - \frac{1}{n} + 4p(nq + 1)}}{2(n + z^2)}\right)$$

and the upper limit is

$$U = 100 \times \min \left( 1, \frac{2np + z^2 + 1 + z\sqrt{z^2 + 2 - \frac{1}{n} + 4p(nq - 1)}}{2(n + z^2)} \right).$$

In addition, if L > p then L = p and if U < p then U = p.

For binary response variables the placebo-adjusted response rates including 95% confidence interval will be derived.

SAS code for risk difference:

proc freq data=;

tables response\* treatment / riskdiff;

run

Note the response value should be sorted with '1' ahead of '0'.

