#### 5.4.2 Crude incidence and related risk estimates

## 5.4.2.1 Crude incidence and $100*(1-\alpha)\%$ confidence interval

For *n* participants, each at risk to experience a certain event with probability  $\pi$ , the crude incidence is estimated as p=x/n, where *x* is the number of participants with the event.

Absolute and relative frequencies will be displayed as well as 95% confidence interval for the relative frequency based on the score method including continuity correction (Newcombe 1998).

With z as  $(1-\alpha/2)$ -quantile of the standard normal distribution (SAS:  $z = PROBIT(1-\alpha/2)$ , n as total number of participants (i.e., number of participants in the denominator), and p as estimated crude incidence (number of participants with event / n) it is q=1-p.

Then the lower limit is

$$L = \max\left(0, \frac{2np + z^2 - 1 - z\sqrt{z^2 - 2 - \frac{1}{n} + 4p(nq + 1)}}{2(n + z^2)}\right)$$

and the upper limit is

$$U = \min\left(1, \frac{2np + z^2 + 1 + z\sqrt{z^2 + 2 - \frac{1}{n} + 4p(nq - 1)}}{2(n + z^2)}\right).$$

In addition, if L > p then L = p and if U < p then U = p.

If appropriate, an exact  $100*(1-\alpha)\%$  confidence interval (Clopper-Pearson, 1934) will be obtained by using the SAS procedure PROC FREQ with the EXACT BINOMIAL statement. However, the confidence interval derived via the score method including continuity correction will be the default in safety analyses.

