## 5.4.2.3 Risk difference and $100*(1-\alpha)\%$ confidence interval

For an investigational drug group with  $n_1$  participants at risk, independent from the control group (e.g., placebo or comparator) with  $n_0$  participants at risk, of whom  $x_1$  and  $x_0$  experience a certain event, the risk difference is estimated as  $p_1-p_0$  with  $p_1=x_1/n_1$  and  $p_0=x_0/n_0$ .

Exact unconditional confidence limits for the risk difference can be obtained with SAS procedure PROC FREQ and option RISKDIFF in the TABLES statement, specifying the RISKDIFF option also in the EXACT statement.

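### The SAP's risk-difference code conditions on response instead of treatment, so it does not return the difference in response rates that the SAP and protocol define

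*SAP*

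**What the plan says.** - SAP 5.4.1 states: "For binary response variables the placebo-adjusted response rates including 95% confidence interval will be derived". The code beneath it is a PROC FREQ table of response by treatment ending in "treatment / riskdiff". A note orders the response values (1 before 0) but gives no order for treatment.
- SAP 5.4.2.3 takes n1 participants at risk on the investigational drug and n0 on control, of whom x1 and x0 "experience a certain event, the risk difference is estimated as" p1 − p0, with p1 = x1/n1 and p0 = x0/n0.
- Protocol 3.2, for the responder endpoints: "Summary measure: difference in proportions between treatments".
- SAP 2.6.2, as revised after early termination, makes the secondary endpoints purely descriptive and says of the binary ones only: "Categorical variables will be presented in frequency tables". It does not mention the risk difference and does not withdraw the sentence in 5.4.1.
- SAP 5.4.1 also gives a confidence interval for a single proportion. Its limits L and U are multiplied by 100, followed by the rule "In addition, if L > p then L = p and if U < p then U = p", where p is a proportion between 0 and 1. SAP 5.4.2.1 prints the same limits and rule for the "95% confidence interval for the relative frequency based on the score method including continuity correction", without the factor 100.

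**The concern.** The first variable in a PROC FREQ table request forms the rows, and RISKDIFF contrasts a column proportion between the two rows. With response first, the output is the share of responders who were in one arm minus the share of non-responders who were in that arm. That describes who the responders were. It is not a difference in response rates. Sorting response 1 ahead of 0 only makes responders the first row; the conditioning is unchanged.

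The direction is also left open. If columns follow alphabetical labels, an arm labelled secukinumab (SAP 2.1) sorts after placebo, and one labelled AIN457 (SAP 2.7.1) sorts before it.

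Three secondary endpoints are binary: a WORC PSD gain of at least 40 points at Week 16 and at Week 24, and a WORC total gain of at least 50 points at Week 16. In a descriptive report the estimates and intervals are the result. A programmer who follows 5.4.1 literally would report a figure that does not match its label or the estimand.

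**Working it through.** **Inputs.** Planning rates of 60% v 35% (PSD40) and 50% v 25% (TOT50), with 117 per arm, come from SAP 3.2. The 21 randomised at termination come from SAP 1. The arm split is not given, so 11 v 10 is an assumption and is varied below. The reading of RISKDIFF, with Wald limits by default, is standard software behaviour and is not described in the documents.

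**The SAP's own figure.** The table "Summary of power for binary secondary endpoints" gives 97% for both Week 16 endpoints. For a difference in response rates, power = Φ{[d − 1.96·√(2p̄(1−p̄)/n)] / √([p1(1−p1)+p0(1−p0)]/n)}. For PSD40, d = 0.25 and p̄ = 0.475, so (0.25 − 1.96 × 0.0653)/0.0632 = 1.93, which is 97.3%. TOT50 gives 98.0%. With a continuity correction they are 96.4% and 97.3%. The stated power therefore agrees with a comparison of response rates between arms.

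**What the code returns.** Let R = x1 + x0 (responders) and M = N − R (non-responders).

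- Correct: x1/n1 − x0/n0.
- Code, secukinumab as column 1: x1/R − (n1 − x1)/M.
- Algebra gives code / correct = n1·n0 / (R·M). The factor is 1 only when R·M = n1·n0. Under 1:1 allocation it equals 0.25/[p̄(1−p̄)].
- With placebo as column 1, the code's value changes sign.

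| Secukinumab v placebo | Correct difference (95% Wald) | Code (95% Wald) | Ratio |
|---|---|---|---|
| 60% v 35%, 117 per arm | 0.250 (0.126 to 0.374) | 0.251 (0.127 to 0.375) | 1.003 |
| 50% v 25%, 117 per arm | 0.250 (0.130 to 0.370) | 0.267 (0.140 to 0.393) | 1.067 |
| 7/11 v 3/10 | 0.336 (−0.066 to 0.738) | 0.336 (−0.066 to 0.738) | 110/(10×11) = 1.000 |
| 3/11 v 1/10 | 0.173 (−0.150 to 0.495) | 0.279 (−0.207 to 0.766) | 110/(4×17) = 1.618 |
| 1/11 v 0/10 | 0.091 (−0.079 to 0.261) | 0.500 (0.281 to 0.719) | 110/(1×20) = 5.500 |
| 6/14 v 2/7 | 0.143 (−0.281 to 0.566) | 0.135 (−0.265 to 0.535) | 98/(8×13) = 0.942 |

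**All 11 v 10 tables.** There are 12 × 11 = 132 tables. The two with no responders or no non-responders are undefined for the code, leaving 130. Weighting by independent binomials at the planning rates:

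| | 60% v 35% | 50% v 25% |
|---|---|---|
| Mean absolute gap, 11 v 10 | 0.013 | 0.030 |
| Chance of a gap above 0.05, 11 v 10 | 6% | 19% |
| Mean gap, splits of 21 from 11:10 to 14:7, either direction | 0.011 to 0.025 | 0.019 to 0.036 |
| Mean gap, arm sizes 7 v 6 to 20 v 20 | 0.007 to 0.023 | 0.024 to 0.042 |

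In 10 of the 130 tables the code's interval excludes 0 when the correct one does not; the reverse never happens. Those 10 tables carry about 0.2% and 0.3% probability at the two sets of planning rates. The sign is right in all 130 tables if secukinumab is column 1 and reversed in all 130 if placebo is.

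**The truncation rule.** Apply the 5.4.1 limits as printed, in percent, and compare them with p as a proportion. For 6/11 the limits are 24.6 and 81.9 and p = 0.545. Since 24.6 > 0.545, the lower limit is overwritten by 0.545. For n = 10 and n = 11 this wrong replacement happens at every count of 1 or more. For 11/11 the limits are 67.9 and 99.2 and p = 1. The upper rule should lift 99.2% to 100%, but 99.2 is not below 1, so the limit stays under the estimate.

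**The case against.** The best counter-argument is that the code may be inoperative. SAP 2.6.2 governs the secondary endpoints and asks only for frequency tables. The document history does not list Section 5 among the parts revised for termination. Appendix 5.4 also still describes covariate-adjusted odds ratios, although no such model remains. This is a plausible inference, but 5.4.1 still says the quantity will be derived and nothing withdraws it.

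Other points stand as limits on size:

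- There is no test, and each arm's responders would appear in the frequency tables, so a reader could recompute the difference.
- The most striking table, 1/11 v 0/10, has probability of about 0.00001 at 60% v 35% and 0.0003 at 50% v 25%. It matters only if true response is well below the planning rates.
- The intended direction can be read from the term placebo-adjusted and from p1 − p0 in 5.4.2.3. It is the code that leaves the sign open; the intention is clear.
- The truncation slip is a separate drafting error in an interval given only where applicable, and a dry run would probably expose it.

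None of this makes the code return the stated quantity. The near-agreement at the planning rates arises because overall response is close to 50% with equal arms.

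**Conclusion.** The point holds. Run as written, the code in SAP 5.4.1 estimates a different quantity from the one named in the sentence above it, in SAP 5.4.2.3 and in Protocol 3.2. It should be corrected, but it is not critical: the affected output is descriptive and no hypothesis test uses it. At the planning rates the expected error is about 0.01 to 0.04 over the arm sizes examined. It grows as overall response moves away from 50%. These sizes rest on assumed arm splits and final denominators, since patients already screened could continue and missing values are not imputed, and on the planning response rates. That the code targets the wrong quantity rests only on standard PROC FREQ behaviour. The truncation rule in 5.4.1 is also wrong as printed.

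**What to change.** Choose one of two routes for the risk difference:

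1. If it is wanted, change the request to `tables treatment*response / riskdiff`, state that secukinumab is row 1 and response = 1 is column 1, and name the output in 2.6.2. Optionally, request the exact unconditional limits already described in 5.4.2.3; these would usually be somewhat wider.
2. If only the frequency tables of 2.6.2 are intended, delete the sentence and code from 5.4.1.

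In either case, put the truncation rule in 5.4.1 on one scale: drop the factor 100 as in 5.4.2.1, or compare the limits with 100p.

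The cost is a swap of two variable names, one line on sort order and one edit to the formula. No new data or further analyses are needed.

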#### 5.4.2 Crude incidence and related risk estimates

## 5.4.2.1 Crude incidence and $100*(1-\alpha)\%$ confidence interval

For *n* participants, each at risk to experience a certain event with probability  $\pi$ , the crude incidence is estimated as p=x/n, where *x* is the number of participants with the event.

Absolute and relative frequencies will be displayed as well as 95% confidence interval for the relative frequency based on the score method including continuity correction (Newcombe 1998).

With z as  $(1-\alpha/2)$ -quantile of the standard normal distribution (SAS:  $z = PROBIT(1-\alpha/2)$ , n as total number of participants (i.e., number of participants in the denominator), and p as estimated crude incidence (number of participants with event / n) it is q=1-p.

Then the lower limit is

$$L = \max\left(0, \frac{2np + z^2 - 1 - z\sqrt{z^2 - 2 - \frac{1}{n} + 4p(nq + 1)}}{2(n + z^2)}\right)$$

and the upper limit is

$$U = \min\left(1, \frac{2np + z^2 + 1 + z\sqrt{z^2 + 2 - \frac{1}{n} + 4p(nq - 1)}}{2(n + z^2)}\right).$$

In addition, if L > p then L = p and if U < p then U = p.

If appropriate, an exact  $100*(1-\alpha)\%$  confidence interval (Clopper-Pearson, 1934) will be obtained by using the SAS procedure PROC FREQ with the EXACT BINOMIAL statement. However, the confidence interval derived via the score method including continuity correction will be the default in safety analyses.

## 5.4.2.2 Odds ratio and $100*(1-\alpha)\%$ confidence interval

For an investigational drug group with  $n_1$  participants at risk, independent from the control group (e.g., placebo or comparator) with  $n_0$  participants at risk, of whom  $x_1$  and  $x_0$  experience a certain event with probability  $\pi_1$  and  $\pi_0$  respectively, the odds ratio is estimated as

$$\frac{p_1/(1-p_1)}{p_0/(1-p_0)}$$
 with  $p_1=x_1/n_1$  and  $p_0=x_0/n_0$ . A conditional exact  $100*(1-\alpha)\%$  confidence interval

can be obtained by using the SAS procedure PROC FREQ with statement EXACT OR. However, to be able to adjust for covariates odds ratios will primarily be obtained from PROC LOGISTIC.

## 5.4.2.3 Risk difference and $100*(1-\alpha)\%$ confidence interval

For an investigational drug group with  $n_1$  participants at risk, independent from the control group (e.g., placebo or comparator) with  $n_0$  participants at risk, of whom  $x_1$  and  $x_0$  experience a certain event, the risk difference is estimated as  $p_1-p_0$  with  $p_1=x_1/n_1$  and  $p_0=x_0/n_0$ .

Exact unconditional confidence limits for the risk difference can be obtained with SAS procedure PROC FREQ and option RISKDIFF in the TABLES statement, specifying the RISKDIFF option also in the EXACT statement.

#### 5.4.3 Exposure adjusted incidence rate and related risk estimates

#### 5.4.3.1 Exposure adjusted incidence rate and $100*(1-\alpha)\%$ confidence interval

It will be assumed that for each of n participants in a clinical trial the time  $t_j$  (j=1,...,n) to the first occurrence of a certain event is observed, or if the event was not experienced, the (censored) time to the end of the observation period. The sequence of first occurrences of an event will be

modeled to follow approximately a Poisson process with constant intensity  $\theta$ . The rate

parameter 
$$\theta$$
 will be estimated as  $\lambda = D/T$ , where  $T = \sum_{j=1}^{n} t_j$  and  $D$  is the number of participants

with at least one event. Conditionally on T, an exact  $100*(1-\alpha)\%$  confidence interval for a Poisson variable with parameter  $\theta T$  and observed value D can be obtained based on (Garwood 1936), from which an exact  $100*(1-\alpha)\%$  confidence interval for D/T will be derived as follows (Sahai 1993):

Lower confidence limit  $L = \frac{0.5c_{\alpha/2,2D}}{T}$  for D > 0, 0 otherwise,

Upper confidence limit 
$$U = \frac{0.5c_{1-\alpha/2,2D+2}}{T}$$

Where  $c_{\alpha,k}$  is the  $\alpha$ th quantile of the Chi-square distribution with k degrees of freedom.

## 5.5 Rule of exclusion criteria of analysis sets

Exclusion due to protocol deviation will be handled through the population attribute of the related estimand. The rules for participant classification in the analysis sets are based on criteria in Table 5-3.

Table 5-3 Criteria leading to exclusion

Analysis Set	Criteria that cause participants to be excluded	
RAS	Not randomized	
FAS	Not in RAS	
	Mistakenly randomized and no double-blind study drug taken	
SAF	No double-blind study drug taken	
PK analysis set	Not in SAF	
	No valid PK (AIN457) concentration measurement	
	PD with impact on PK data	

## 5.6 Computation of T-score for PROMIS SF UE

Please use the following table to convert Raw PROMIS value into T-score.

Raw summed score	T-Score	Raw summed score	T-Score
7	16.3	22	33.9
8	19.3	23	34.7
9	21.1	24	35.6
10	22.6	25	36.6
11	23.9	26	37.5
12	25.0	27	38.6
13	26.1	28	39.7
14	27.0	29	40.9

15	27.9	30	42.3
16	28.8	31	43.9
17	29.7	32	45.6
18	30.5	33	47.7
19	31.4	34	50.9
20	32.2	35	58.2
21	33.0		

